- 474 3. To determine whether energy deficit increases appetite, and alters food preferences
475 and biological mediators of appetite (i.e., appetite-mediating hormones and
476 gastrointestinal transit time) during a simulated 72-h SUSOPS, and identify effects
477 on food choice following SUSOPS.
- 478
- 479 4. To determine the effects of a simulated 72-h SUSOPS on physical performance,
480 mood, cognitive performance, vigilance assessed continuously, and nightly sleep
481 quality and determine whether energy deficiency exacerbates the effects of
482 SUSOPS.
- 483
- 484 5. Characterize genomic and epigenomic stress markers in blood and saliva,
485 particularly markers interacting with the microbiome from gut and saliva, to build
486 networks that identify the “interactome” response associated with changes in energy
487 homeostasis during SUSOPS.

488

489 **Hypotheses**

490

- 491 1. SUSOPS will increase circulating concentrations of IL-6 and hepcidin and decrease
492 fractional iron absorption.
- 493
- 494 2. Energy balance will attenuate circulating concentrations of IL-6 and hepcidin and

495 improve fractional iron absorption compared to severe energy deficit.

496

497 **Secondary Hypotheses**

498

499 1. Energy balance will attenuate muscle glycogen depletion, intramuscular
500 inflammation, minimize upregulation in microRNA transcription, facilitate muscle
501 remodeling, and limit negative protein balance, and decrements in immune function.

502

503 2. Energy balance will attenuate increases in intestinal permeability, increases in
504 gastrointestinal transit time, increases in markers of gut damage, and changes in gut
505 microbiota composition and function during SUSOPS.

506

507 3. Energy deficit will increase appetite, change food preferences, increase circulating
508 concentrations of appetite-suppressing hormones, and suppress circulating
509 concentrations of appetite-stimulating hormones during SUSOPS, and alter food
510 choices following SUSOPS.

511

512 4. SUSOPS will negatively impact physical performance, mood, cognition, and
513 vigilance, and SUSOPS also will alter the sleep quality of participants. Negative
514 energy balance will exacerbate the effects of SUSOPS on these parameters.

515

516 5. A systems biology approach integrating multi-omics data derived from fecal, blood,
517 and saliva will elucidate genetic targets within host-microbiome relationship

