715 exercise [64] and the compendium of metabolic equivalents for physical activities (refer to
716 descriptions of Determination of Peak Oxygen Consumption and SUSOPS BAL and SUSOPS
717 NEG BAL below) [65].
718

719 For example, an 85 kg individual with a baseline total daily energy requirement (RMR of 2000
720 kcal/d * 1.3) of 2600 kcal/d and a VO_{2peak} of 45 mL/kg/min, would expend approximately 2468
721 kcal during two, 90-min load carriage exercise bouts combined [i.e., 85kg+32kg load = 117 kg *
722 (~50% of VO_{2peak} is 6.7 METS *3.5 mL/kg/min)/1000] * (90 min of work * 5 kcal/L/min) = 1234
723 kcal/exercise bout], 600 kcal during a 60-min unloaded exercise session (calculations follow the
724 same format), and approximately 100 kcal/d performing the Warfighter tasks, for an estimated
725 TDEE of ~5768 kcal/d. TDEE prescriptions are individualized to each volunteer's requirements
726 and will be held constant between SUSOPS 1 and 2. Exercise intensities, total duration
727 exercised, and TDEE will likely differ between volunteers. Every attempt will be made to
728 maintain TDEE between 5000-6000 kcal/d across all volunteers; however, some individuals
729 may expend more and others less.
730

731 Registered Dietitians will develop individualized daily menus for SUSOPS 1 and 2 using Food
732 Processor SQL (ESHA Research, Salem, OR, Version 10.14). The diets during each SUSOPS
733 period will be derived primarily from components of the US military Meals Ready-to-Eat (MRE)
734 rations to achieve appropriate macronutrient proportions. The macronutrient distribution of the
735 MRE-based diets will not be manipulated. Thus, volunteers will be consuming a diet providing
736 approximately 60% carbohydrate, 10-15% protein, and 25-30% fat. The macronutrient
737 distribution, as a % of total energy, will remain constant during SUSOPS NEG BAL by uniformly
738 reducing total energy intake across carbohydrate, protein, and fat. This feeding paradigm will
739 most closely resemble field-feeding practices observed during recent USARIEM studies [55,
740 66]. The micronutrient content of the ration will not be altered. However, to limit the potential
741 confounding effect of differing iron intakes across SUSOPS 1 and 2, volunteers will consume
742 supplemental iron sulfate mixed in water (Ferrous sulfate drops, RxChoice, available OTC)
743 during SUSOPS NEG BAL to match total iron consumed during SUSOPS BAL. This equates to

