744 only ~4-10 mg supplemental iron and will be consumed with one meal each day to mimic iron
745 intake during SUSOPS BAL (iron content of SUSOPS BAL is approximately 20-25 mg/d). Water
746 will be allowed ad libitum and total amount consumed will be recorded by study team members.
747 During the 48 hours prior to each SUSOPS period (beginning on days 1 and 11, volunteers will
748 be fed meals derived of commercially available foods which will meet calculated energy
749 requirements to maintain their body weight.
750

751 Volunteers will receive instructions from study dietitians on how to consume an ad libitum diet
752 with the same macronutrient distribution during the two recovery periods (see "Choosing Your
753 Foods During Recovery" document). Food records will be maintained by study volunteers on
754 days 6-8 and 16-18. Volunteers will meet with study dietitians to review these records. These
755 records will be used to determine how energy deficit during SUSOPS impacts food selection
756 during recovery. Physical activity will be restricted during both recovery periods.
757

758 **Determination of Total Daily Energy Expenditure**

759 Doubly labeled water (DLW) will be used to determine actual TDEE during SUSOPS 1 and
760 SUSOPS 2 and verify the accuracy of estimated TDEE. DLW will be administered during the first
761 iron study on day 2 (~0000 h after an 8 h fast). Immediately before drinking the DLW, volunteers
762 will provide a urine sample to determine the natural abundance of ^{18}O and ^2H . They will not eat or
763 drink anything for 4 h (~0400 h) after consuming a total of 120 g DLW containing 10% H_2^{18}O
764 (~0.285 g $\text{H}_2^{18}\text{O}\cdot\text{kg}$ total body water $[\text{TBW}]^{-1}$) and 99% $^2\text{H}_2\text{O}$ (~0.15 g $^2\text{H}_2\text{O}\cdot\text{kg}$ TBW^{-1} ; Sigma-
765 Aldrich, St. Louis, MO or similar company). The DLW dose container will be rinsed with local tap or
766 bottled water, which the volunteer will drink. Urine samples will then be collected approximately 4 h
767 and 6 h after the DLW dosing for initial TBW determinations to be made. Volunteers will be free to
768 eat and drink after these urine samples.

769
770 Two volunteers will be chosen at random to consume only locally available drinking water to control
771 for natural changes in ^2H and ^{18}O abundance (local water will be analyzed to determine isotopic

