1487 significant phase-by-time interactions are observed post hoc comparisons will be made
1488 using paired t-tests with Bonferroni corrections.

1489

1490 **Secondary Objectives**

1491 Linear mixed models will be used to examine changes in intestinal permeability and
1492 gastrointestinal transit time. Models will include subject as a random factor, and study
1493 phase as a fixed factor. To test for carryover effects a main effect of group (SUSOPS
1494 BAL first, SUSOPS NEG BAL first) and a group-by-phase interaction will be included in
1495 initial models. These terms will be removed if they do not significantly contribute to the
1496 overall fit of the model. When a significant main effect is observed post hoc
1497 comparisons will be made using paired t-tests with Bonferroni corrections.

1498

1499 Fecal metabolomics data will be visualized using hierarchical average-linkage clustering
1500 and principal components analysis. Bacterial taxonomic data will be visualized using
1501 hierarchical average-linkage clustering and principal coordinates analysis of beta (i.e.,
1502 between samples) diversity scores (e.g., Bray-Curtis, and weighted and unweighted
1503 UniFrac). Alpha (i.e., within-sample) diversity will be calculated for taxonomic data using
1504 Shannon, Simpson and Chao1 indices. Linear mixed models will be used to examine
1505 changes in biomarkers of gut health, fecal metabolite concentrations, and alpha diversity
1506 over time. Models will include subject as a random factor, and study phase, time within
1507 phase, and their interaction as fixed factors. To test for carryover effects a main effect of
1508 group (SUSOPS BAL first, SUSOPS NEG BAL first) and a group-by-phase interaction
1509 will be included in initial models. These terms will be removed if they do not significantly
1510 contribute to the overall fit of the model. Models for bacterial taxa and gene abundance
1511 will be analyzed using the R statistical software package “DESeq2” or equivalent. The
1512 Benjamini-Hochberg correction will be used to control the false discovery rate in
1513 microbiome-specific and metabolite models. Data analysis will be completed using
1514 SPSS, XLSTAT, R, Qiime, or similar software as needed.

1515

1516 Linear mixed models will be used to examine changes in appetite-mediating hormone
1517 concentrations, appetite ratings, food preferences, food choice during recovery (i.e., diet

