1518 macronutrient proportion and energy intake). Models will include subject as a random
1519 factor, and study phase, time within phase, and their interaction as fixed factors.
1520 Separate analysis will be conducted for fasted and post-exercise appetite-mediating
1521 hormones. To test for carryover effects a main effect of group (SUSOPS BAL first,
1522 SUSOPS NEG BAL first) and a group-by-phase interaction will be included in initial
1523 models. These terms will be removed if they do not significantly contribute to the overall
1524 fit of the model. When significant phase-by-time interactions are observed post hoc
1525 comparisons will be made using paired t-tests with Bonferroni corrections.

1526

1527 The mRNA seq strand-specific libraries will be assayed using the Illumina HiSeq
1528 platform. Paired end reads of the strand-specific RNA sequences (RNA-Seq) will be
1529 generated using NextSQ from one flow cell with eight lanes, producing at least 30 million
1530 reads of 100 bases per sample. Based calling and expression analysis will be conducted
1531 using the Illumina-provided tool CASAVA. miRNA (20-40 bp) will be size selected from
1532 total RNA and will be processed by Illumina NextSQ. Image analysis and base calling
1533 will be performed using the newest available version of the Illumina pipeline.

1534 Preprocessing of raw base calls and sample de-multiplexing will be performed using the

1535 standard open source tool CASAVA. The microRNA read count matrix will be generated
1536 by a series of tool kits of latest version including CutAdapt, short read aligner Bowtie and
1537 PICARD. Metabolomics and proteomics reads will be processed by the software offered
1538 by the vendors namely Waters Corporation and BioRad, respectively.
1539

1540 Using a systems approach, we will integrate multiple levels of biological information. We
1541 have published the analysis pipeline and implemented it successfully in the past. Our
1542 pipeline uses industry standards and our established SOPs. We will start by analyzing
1543 and processing data at the analyte level for each data type such as mRNA expression,
1544 miRNA expression, microbiome, proteomics, and metabolomics. We will first examine
1545 the confounding factors or batch effects caused by non-biological factors, such as the
1546 technical error, sample processing date etc., using principal component analysis and

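### Recovery macronutrient proportion is both an instructed condition and a tested food-choice outcome, so a null on that component cannot be read as no effect of energy deficit

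*Combined protocol and SAP*

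**What the plan says.** **The instruction.** B5.3, in the subsection on diet and energy expenditure prescription: "Volunteers will receive instructions from study dietitians on how to consume an ad libitum diet" "with the same macronutrient distribution during the two recovery periods". It is supported by a handout on choosing foods during recovery. The only macronutrient distribution given earlier in that subsection is that of the ration diet, "approximately 60% carbohydrate, 10-15% protein, and 25-30% fat".

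**The use of the records.** The next sentences of the same paragraph have volunteers keep food records on days 6-8 and 16-18. "Volunteers will meet with study dietitians to review these records". Their purpose follows: the "records will be used to determine how energy deficit during SUSOPS impacts food selection" during recovery.

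**The hypothesis.** Secondary objective 3 in B4 includes effects on food choice after SUSOPS. Secondary hypothesis 3 predicts that energy deficit will affect "concentrations of appetite-stimulating hormones during SUSOPS, and alter food" choices after SUSOPS.

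**The analysis.** B5.8.2, Secondary Objectives, lists among the outcomes for linear mixed models "concentrations, appetite ratings, food preferences, food choice during recovery (i.e., diet" "macronutrient proportion and energy intake"). The fixed factors are study phase, time within phase and their interaction.

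**The concern.** A quantity that volunteers are asked to keep the same after both SUSOPS periods cannot also serve as a clean measure of what they would have chosen. The instruction is given identically after BAL and NEG BAL, so it works directly against the within-subject contrast that the model is meant to estimate.

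What is at stake is how a null is read. If macronutrient proportion does not differ by phase, the plan as written allows the conclusion that energy deficit does not alter the composition of the recovery diet. The same result would arise if volunteers had simply done as they were told. B2 presents food choice after SUSOPS as relevant to weight regain, so the misreading would bear on a stated purpose of the study, although a secondary one.

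**Working it through.** The plan gives no figure for this outcome, so there is none to reproduce. B5.8.1 covers appetite-mediating hormones but gives no effect size, SD or power for recovery diet composition. The check is therefore a comparison of passages, with one line of algebra for the direction.

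**1. What is instructed and what is measured.**

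| Component of recovery food choice (B5.8.2) | Status under the B5.3 instruction |
|---|---|
| Diet macronutrient proportion | Instructed to be the same |
| Energy intake | Ad libitum, not constrained |

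The conflict is confined to the first row.

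**2. Direction.** Write F_B and F_N for the proportions a volunteer would choose freely after BAL and after NEG BAL, T for the instructed target, and a for the share of the gap to the target that following the instruction closes. The observed proportion is

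O = aT + (1 − a)F.

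With the same a in both phases,

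O_N − O_B = (1 − a)(F_N − F_B).

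The difference is intact at a = 0 and zero at a = 1. If a differs by phase, T no longer cancels and the contrast mixes choice with adherence.

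**3. Ambiguity of the target.** The instruction may mean the same as the ration diet, or the same in both recoveries. Under the second reading the target in Recovery 2 is the volunteer's own Recovery 1 diet, F_1. Then O_2 = aF_1 + (1 − a)F_2, so O_2 − F_1 = (1 − a)(F_2 − F_1). The shrinkage is the same under either reading.

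**4. Which recorded days are covered.** B5.3 (Experimental Design) places Recovery 1 on days 7-12 and Recovery 2 on days 17-22. The records cover days 6-8 and 16-18. On those definitions days 7, 8, 17 and 18 fall under the instruction, while days 6 and 16 may not. The diet paragraph nevertheless treats all the records as describing food selection in recovery, so the point is unsettled.

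**5. Whether another measure fills the gap.** The Leeds Food Preference Questionnaire is given on days -1, 5 and 15, none of them in recovery. The food records are the only planned source on diet composition after SUSOPS.

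**6. Whether the plan reconciles the two.** No section exempts the recorded days from the instruction or explains how choice is to be inferred under it.

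**The case against.** The strongest reply is that the diet is ad libitum and self-selected, so composition is guided rather than fixed. The wording that matters is in a handout that is not in the documents, and days 6 and 16 may be free of it. This stands. A reader might infer that the instruction abolishes the outcome; the documents support only attenuation of unknown degree. A difference that appeared despite the instruction would still be informative.

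A reader might also want to attach a loss of power. The documents do not support one. There is no effect size, SD or adherence figure for this outcome, and the answer turns on an assumption about variance. If following the instruction shrinks the mean difference by (1 − a) and leaves the SD of the difference alone, the standardised effect falls by (1 − a). If the SD shrinks in proportion, the standardised effect does not change for any a below 1. Nothing in the plan chooses between these.

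Standardising diet in recovery is also a defensible choice in a crossover. Table 1 (B5.4) shows IL-6, hepcidin and iron sampled on days 7, 8, 17 and 18. This stands as well, and it bears on which remedy to prefer. It does not make macronutrient proportion interpretable as choice.

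Finally, this is one component of one secondary outcome. Energy intake, appetite ratings, hormones and the food preference questionnaire are not affected by this point. That limits its weight but does not remove the contradiction.

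**Conclusion.** The contradiction is explicit within one paragraph of B5.3 and is carried into B5.8.2. To the extent volunteers follow the recovery instruction, the BAL versus NEG BAL difference in macronutrient proportion is pushed toward zero, and a null on that component does not show that energy deficit leaves food choice unchanged. The direction assumes similar adherence after the two phases. The degree cannot be judged from the documents and no number should be put on it. Recovery energy intake remains a valid test of the recovery part of secondary hypothesis 3, and the primary objectives are not affected.

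**What to change.** In B5.8.2, remove recovery macronutrient proportion from the food-choice test. Report it descriptively by phase, as adherence to the recovery diet instruction. Test the recovery food-choice element of secondary hypothesis 3 on energy intake. Align the B5.3 sentence on the purpose of the food records, and state there whether the instruction applies on days 6 and 16.

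The cost is wording and the loss of one component of a secondary outcome. Dietary standardisation is kept in full.

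The alternative is to withhold the macronutrient instruction on the recorded days, which would keep composition as an outcome. It is a trade-off and should not be presented as cost-free: diet composition could then differ by phase on days 7, 8, 17 and 18, when IL-6, hepcidin and iron are sampled. The meals provided in the 48 h before each SUSOPS control entry to SUSOPS 2 but do not protect those recovery samples.

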189 period (Recovery 2). During SUSOPS, subjects will be randomized to consume either sufficient
190 food (combat rations) to maintain energy balance within $\pm 10\%$ of estimated total daily energy
191 expenditure (SUSOPS BAL) or will be provided only enough food to match 45% of total daily
192 energy expenditure to elicit severe negative energy balance (SUSOPS NEG BAL). Testing
193 procedures and primary outcome measures include dual energy x-ray absorptiometry (DEXA),
194 maximal and sub-maximal aerobic exercise testing, load carriage exercise, controlled feeding,
195 stable isotope assessments of energy expenditure, fractional iron absorption and whole-body
196 protein turnover, percutaneous muscle biopsies to assess intramuscular IL-6, glycogen status,
197 and regulators of muscle remodeling and substrate metabolism, intestinal permeability, gut
198 microbiome composition and function, and blood sampling to assess circulating concentrations
199 of IL-6 and other biomarkers of inflammation, muscle damage, nutritional, metabolic stress, and
200 immune responses to SUSOPS BAL and NEG BAL. Physical performance will be assessed
201 before and after each SUSOPS and during each recovery period using the vertical jump test.
202 Self-reported mood, sustained attention, and cognitive performance will be assessed twice daily
203 using the Profile of Mood States, the Psychomotor Vigilance Task, the Evaluation of Risk
204 Questionnaire, the Match-to-Sample task, the Grammatical Reasoning test, and the N-Back
205 task. Overall vigilance and nighttime sleep quality will be assessed via the wrist-worn
206 USARIEM Vigilance Monitoring System, the Fatigue Science Readiband™ actigraph, Philips
207 Respironics Actiwatch® Spectrum Plus, or equivalent device. This design will test the
208 hypothesis that maintaining energy balance will attenuate the IL-6 response to SUSOPS,
209 improve iron absorption, and attenuate the potential negative effects of excessive inflammation
210 on whole-body metabolic homeostasis. Risks include those associated with venous
211 catheterization, venipuncture, muscle biopsies, DEXA, exercise, and the discomfort of severe
212 underfeeding.

[figure not shown]
214 **B2. BACKGROUND AND SIGNIFICANCE**

216 **Physiology of the Inflammatory Response to Exercise**

217 Prolonged strenuous exercise is characterized by a large increase in circulating concentrations

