 604 and be provided a 48 h carbohydrate refeeding diet on days 1 and 2 to restore muscle glycogen
 605 content pre-SUSOPS (**Figure 3**). On day 2, following an ≥ 8 h fast (0000 h), volunteers will
 606 undergo the first of three fractional iron absorption studies (Iron
 607 Study 1), during which time volunteers will ingest a stable isotopically labeled iron ($^{54}\text{FeSO}_4$)
 608 drink followed by serial blood draws over the next 6 h. A fasting blood draw and percutaneous

609 muscle biopsy of the vastus lateralis will be collected on the morning of day 3. Volunteers will
610 also complete approximately 3-4 mood/cognitive-performance familiarization sessions and 1
611 baseline session before the SUSOPS testing period. Immediately thereafter, volunteers will
612 complete a 72-h SUSOPS, and will be provided either sufficient food (combat rations) to
613 maintain energy balance within $\pm 10\%$ of estimated total daily energy expenditure (SUSOPS
614 BAL) or only enough food to match 45% of total daily energy expenditure to elicit severe
615 negative energy balance (SUSOPS NEG BAL). Volunteers will reside at the Doriot Climatic
616 Chambers during the SUSOPS beginning the evening of days 1 and 11 (volunteers will be
617 provided standardized meals), and ending after final data collection on days 6 and 16.
618 Throughout these periods, volunteers will wear the USARIEM Vigilance Monitoring System, the
619 Fatigue Science Readiband™ actigraph, Philips Respironics Actiwatch® Spectrum Plus, or
620 equivalent device on their non-dominant wrist. The activities performed will be comprised of
621 load carriage and unloaded steady-state exercise and Warfighter operational tasks (e.g., 15 m
622 timed casualty evacuation drag of a 123 kg dummy, move under fire, prepare fighting positions)
623 to increase total daily energy expenditures. Physical performance will be assessed before and
624 after each SUSOPS. Mood, cognitive performance and overall vigilance will also be assessed.
625 Sleep will be restricted to four hours per night during SUSOPS to mimic recent field studies. On
626 day 6, immediately following the final exercise bout and 8 h after dinner on day 5, a second
627 muscle biopsy will be collected (alternate leg from biopsy one) and volunteers will undergo Iron
628 Study 2 ($^{57}\text{FeSO}_4$). Days 7-12 will serve as a recovery period from SUSOPS 1 (Recovery 1).

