772 enrichments). Rate of disappearance of ^{18}O and ^2H for volunteers dosed with DLW will be
773 corrected for mean changes in background enrichments based on controls. Morning urine samples
774 will be collected daily during each SUSOPS period to determine elimination rates over time. TBW
775 will be calculated by determining the regression line for the elimination of ^2H and ^{18}O and
776 extrapolated to a maximum enrichment. All urine samples will be collected and stored in 5ml tubes
777 and shipped to the Pennington Biomedical Research Center (PBRC) for analysis.

778
779 Enrichments of ^2H and ^{18}O will be measured using isotope ratio mass spectroscopy (Finnigan Mat
780 252, Thermo Fisher Scientific, Waltham, MA or similar model). The ^2H and ^{18}O isotope elimination
781 rates (k_{H} and k_{O}) will be calculated by linear regression using the isotopic disappearance rates
782 during each training phase.

$$783 \quad r\text{CO}_2 = (\text{N}/2.078)(1.01k_{\text{O}} - 1.04k_{\text{H}}) - 0.0246r\text{H}_2\text{O}_f$$

784
785 where N is TBW; k_{O} and k_{H} are ^{18}O and ^2H isotope disappearance rates respectively, and $r\text{H}_2\text{O}_f$
786 is the rate of fractionated evaporated water loss and is estimated to be $1.05 \text{ N} * (1.01 k_{\text{O}} - 1.04$
787 $k_{\text{H}})$. Total daily energy expenditure will then be calculated using the energy equivalent of CO_2
788 for a respiratory quotient of 0.86 [68].

790 **Anthropometric Data**

791 Anthropometrics and body composition will be performed using standardized techniques and
792 equipment to characterize study volunteers, and evaluate responses to SUSOPS 1 and 2.
793 Height will be measured in duplicate to the nearest 0.1 cm using a stadiometer at baseline.
794 Body weight will be measured, nude (scale will be placed in a locked bathroom) and after an
795 overnight fast (≥ 8 h), using a calibrated digital scale to the nearest 0.1 kg at baseline (days -14-
796 0) and then daily throughout the 22 d study to ensure weight maintenance and/or weight loss.

797
798
799 Body composition will be determined on days 2, 6, 12, and 16 using a four-compartment model
800 derived from dual energy x-ray absorptiometry (DEXA, DPX-IQ, GE Lunar Corporation,
801 Madison, WI) and bio-electrical impedance (InBody 720, BIOSPACE, Korea) [69]. The DEXA
802 technique allows for the non-invasive assessment of soft tissue composition by region with a

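### One respiratory quotient (0.86) for both diets biases doubly labelled water expenditure in opposite directions, by an estimated 4.5 to 10 points between BAL and NEG BAL under assumed fuel constants

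*Combined protocol and SAP*

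**What the plan says.** All of this is in the combined protocol and SAP, section B5.3 unless noted.

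- **Purpose of the measurement.** "Doubly labeled water (DLW) will be used to determine actual TDEE during SUSOPS 1 and" SUSOPS 2, and to verify the estimated value.
- **Conversion.** Isotope elimination rates are fitted "during each training phase", so CO2 production is specific to each period. Expenditure is then obtained from the energy equivalent of CO2 "for a respiratory quotient of 0.86". No second value, correction for oxidised body stores or sensitivity analysis is described.
- **Diet.** The ration supplies "approximately 60% carbohydrate, 10-15% protein, and 25-30% fat". The "distribution, as a % of total energy, will remain constant during SUSOPS NEG BAL by uniformly" cutting total energy. NEG BAL provides "only enough food to match 45% of total daily energy expenditure".
- **Expenditure.** It is meant to be matched between the two diets, and its prescription is held constant across SUSOPS 1 and 2. The worked example is about 5768 kcal/d.
- **Analysis.** B5.8.2 plans correlation and multiple regression among study outcomes.

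**The concern.** Doubly labelled water measures CO2, not energy. The energy released per litre of CO2 depends on the fuel: it is lowest for carbohydrate and highest for fat. Holding the ration's percentages constant does not make the fuel constant, because in NEG BAL more than half of what is burned is not ration. A single quotient lying between the two true values overstates expenditure in BAL and understates it in NEG BAL.

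The crossover does not cancel this error. It follows the diet, not the man or the period, so within-man comparison and randomised order leave it intact.

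Three things are at stake. Expenditure that was truly matched would read as unmatched, and could be taken for a metabolic fall under deficit. The comparison of estimated with measured expenditure would be off in a different direction for each diet. The achieved deficit would read too small, and any regression on measured energy balance would carry an error tied to diet.

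**Working it through.** **1. The plan's own base figure.** One load-carriage bout: 117 kg × 6.7 × 3.5 / 1000 × 90 min × 5 kcal/L = 1234.6 kcal. The plan uses 1234, so two bouts are 2468. Total: 2600 + 2468 + 600 + 100 = 5768 kcal/d, as stated. The plan gives no derivation of 0.86.

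**2. Assumptions not in the documents.**
- Energy per litre of CO2 (Weir form): E(RQ) = 3.941/RQ + 1.106.
- Quotient and kcal per litre of O2: carbohydrate 1.00 and 5.05; fat 0.707 and 4.69; protein 0.82 and 4.48.
- Body stores in NEG BAL: either all fat, or 10% protein with 0 to 40% glycogen and the rest fat.

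**3. BAL quotient (intake equal to expenditure).** Per 100 kcal of a 60/10/30 ration (carbohydrate/protein/fat):
- O2 = 60/5.05 + 10/4.48 + 30/4.69 = 11.88 + 2.23 + 6.40 = 20.51 L.
- CO2 = 11.88 × 1.00 + 2.23 × 0.82 + 6.40 × 0.707 = 18.23 L.
- Quotient = 18.23/20.51 = 0.889. For 60/15/25 it is 0.895.

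**4. NEG BAL quotient.** Fuel = 45% ration + 55% body stores. Example: 60/10/30 ration, stores 20% glycogen, 10% protein, 70% fat.
- Carbohydrate: 0.45 × 60 + 0.55 × 20 = 38. Protein: 10. Fat: 0.45 × 30 + 0.55 × 70 = 52.
- O2 = 7.52 + 2.23 + 11.09 = 20.84 L; CO2 = 17.19 L; quotient = 0.825.

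**5. Bias.** Reported/true = E(0.86)/E(true RQ), with E(0.86) = 5.689.
- BAL: 5.689/5.539 (RQ 0.889) = +2.7%; 5.689/5.511 (RQ 0.895) = +3.2%.
- NEG BAL in the example: 5.689/5.884 = −3.3%.

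The gap is BAL bias minus NEG BAL bias. The deficit read is 1 − 0.45/(reported/true), against a true 55%. Ranges cover the two ration compositions.

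| Body-store fuel in NEG BAL | NEG BAL RQ | NEG BAL bias | Gap, points | Gap at 5768 kcal/d | Deficit read |
|---|---|---|---|---|---|
| All fat | 0.787–0.790 | −6.9 to −6.7% | 9.6–9.9 | 556–572 | 51.7–51.8% |
| 10% protein, 90% fat | 0.794–0.796 | −6.3 to −6.1% | 9.0–9.3 | 520–536 | 52.0–52.1% |
| 10% glycogen | 0.809–0.812 | −4.8 to −4.6% | 7.5–7.8 | 434–450 | 52.7–52.9% |
| 20% glycogen | 0.825–0.827 | −3.3 to −3.1% | 6.0–6.3 | 347–363 | 53.5–53.6% |
| 30% glycogen | 0.841–0.843 | −1.8 to −1.6% | 4.5–4.8 | 260–277 | 54.2–54.3% |
| 40% glycogen | 0.857–0.859 | −0.3 to −0.1% | 3.0–3.3 | 174–190 | 54.9–55.0% |

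**6. Less favourable cases.** If BAL is fed at only 90% of expenditure, with the shortfall met by 90% fat and 10% protein, its quotient falls to 0.871–0.876. The gap is then 4.4–4.6 points at 20% glycogen, 2.9–3.1 at 30% and 1.4–1.6 at 40%.

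**7. When the gap vanishes.** With BAL in balance, this needs body stores to supply fuel in the same proportions as the ration, about 60% carbohydrate. The three-day deficit is 0.55 × 5768 × 3 = 9517 kcal. At an assumed 4 kcal/g, 60% of that is about 1.4 kg of glycogen; 20% is about 480 g and 40% about 950 g.

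**8. Other energy constant.** Using the plan's own 5 kcal per litre of O2, so E = 5/RQ, the gap for 0 to 30% glycogen is 5.6 to 12.2 points. The Weir form is the more cautious choice.

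**The case against.** The strongest reply is that the quotient touches only a verification measure. Much of that stands, and it rules out several stronger readings.

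- **Feeding.** A reader might infer that a wrong expenditure means wrong feeding. The documents do not support this. Intake is prescribed from estimated expenditure (resting metabolic rate × 1.3 plus calculated exercise cost), and the water measurement only verifies that estimate.
- **The ±10% tolerance.** A reader might set the gap against this limit. It applies to BAL alone and is defined on estimated expenditure. The BAL error is only about 3%, and most of the larger gaps is NEG BAL error.
- **Primary outcome.** The abstract (B1) includes "stable isotope assessments of energy expenditure, fractional iron absorption and whole-body" protein turnover in a list headed as procedures and primary outcome measures. That list also contains DEXA and controlled feeding. The objectives and hypotheses in B4 name IL-6, hepcidin and iron absorption; none concerns expenditure, and B5.8.2 does not name it as a tested outcome.
- **A larger gap.** A NEG BAL quotient of 0.78 against 0.89 in BAL would give 10.4 points (601 kcal/d). With 45% of energy from this ration, even all-fat body stores give about 0.787, so 0.78 is out of reach under the stated constants.
- **Diet contrast.** A deficit read as 52 to 54% instead of 55% is still severe. The manipulation is not in doubt.
- **Glycogen.** The men start each SUSOPS after carbohydrate refeeding, so glycogen will meet part of the shortfall and the gap may sit toward the lower end.

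The reply does not remove the bias. No passage supplies a second quotient, and the direction follows from the design across the mixes in the table. A known error tied to diet in a reported quantity is worth correcting when the data to do so are already collected.

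**Conclusion.** The point holds as a modest, correctable bias in measured expenditure and in energy balance derived from it. For 0 to 30% of the shortfall from glycogen, BAL reads about 3% high and NEG BAL about 2 to 7% low. The gap is about 4.5 to 10 points, falling to about 3 at 40% glycogen and to about 1.5 if BAL is also fed at 90%.

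The single quotient, the 45% intake and the ration mix are stated in the plan. The size rests on the assumed fuel constants and endogenous mix and should be quoted as a range. The consequences are confined to the matching check, the check of estimated expenditure, the achieved deficit and any regression on measured energy balance. The IL-6, hepcidin and iron absorption measurements do not change.

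**What to change.** - **BAL:** use the food quotient computed from recorded intake.
- **NEG BAL:** use one phase-level quotient combining recorded intake (45%) with a stated endogenous fuel mix (55%). Inform the mix from group-mean body composition change, muscle glycogen from the biopsies, and urinary nitrogen, all already collected.
- **Reporting:** give expenditure and energy balance over NEG BAL quotients of about 0.79 to 0.86, and keep 0.86 in both phases as a sensitivity analysis. State the rule before the expenditure data are analysed.

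The cost is a small change in calculation, with no new procedure. The downside is that the NEG BAL quotient depends on an assumed fuel mix, so it cannot be presented as a single exact value.

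The scans should not drive a man-by-man correction. They fall on days 2 and 12, a day before each SUSOPS starts, and again on days 6 and 16, so they do not bracket the 72 hours. DEXA precision is given as 1 to 3%, while the whole three-day deficit is worth about 1 kg of fat (9517 kcal at an assumed 9.4 kcal/g). An individual correction could add more noise than the bias it removes.
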